11.0 Statistical/Data Analysis Plan

11.1 Statistical Considerations:

List the statistical methods to be used to address the primary and secondary objectives, specific aims, and/or research hypotheses. Explain how missing data and outliers will be handled in the analysis. The analysis plan should be consistent with the study objectives. Include any sub-group analyses (e.g., gender or age group). Specify statistical methods and variables for each analysis. Describe how confounding variables will be controlled in the data analysis

To determine the effect of low back pain education (cautionary vs resiliency) on deadlift performance (weight lifted), we will use ANOVA and planned comparison analysis if between-group differences are found between groups.

To determine the effect of low back pain education on deadlift self-efficacy, we will analyze change scores with a one-way ANOVA and planned comparisons if significant.

To determine the effect of low back pain education on perceived spine vulnerability, we will analyze change scores with a one-way ANOVA and planned comparisons if significant.

Our study design accounts for some confounding factors by utilizing randomization. Potentially confounding variables should be balanced between groups. We will test groups at baseline to ensure they are similar among important characteristics. Furthermore, characteristics that are different among groups at baseline or that appear to be influential on load lifted will be included in the ANOVA model as a covariate to control for and test for potential confounding.

11.2 Sample Size:

1200 participants

11.3 Total number of subjects requested (including records and specimens):

1200

11.4 If you are recruiting by study arm, please identify the arms of the study and how many subjects will be enrolled in each arm

N/A

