2. Dependent Variables: performance outcome by event including 1) successful completion (pass/fail), 2) basic rifle marksmanship qualification score, 3) 12-mile road march outcome (pass/fail), 4) Army Combat Fitness Test (ACFT) score, 5) land navigation score, 6) swimming assessment outcome (pass/fail) and 7) any other individually-graded events.

6. Determine the effect of low back pain education (cautionary vs resiliency) on deadlift performance (weight lifted).

We will analyze this with MDL weight lifted as the dependent variable (one-way ANOVA), with a planned comparison analysis if significant differences are found between groups.

7. Determine the degree of confidence cadets have in their ability to succeed at the MDL both before and after the education and MDL

We will analyze if there is a main effect of time in the pre-to-post self-efficacy scores with a paired t-test. We will use multiple regressions to analyze the impact of self-efficacy scores on MDL performance.

8. Determine the effect of low back pain education (cautionary vs resiliency) on deadlift self-efficacy. We will analyze change scores with one-way ANOVA with planned comparisons between groups if ANOVA is significant.

9. Determine the effect of low back pain education (cautionary vs resiliency) on perceived spine vulnerability on a deadlift.

We will analyze change scores with one-way ANOVA with planned comparisons between groups if ANOVA is significant.

9.4 Study Design:

Describe study design in one to two sentences (e.g., prospective, use of existing records/data /specimens, observational, cross-sectional, interventional, randomized, placebo-controlled, cohort, etc.). Specify the phase - Phase I, II, III, or IV- for FDA-regulated investigational drug research

This study will be a randomized controlled trial with parallel design and 1:1 allocation ratio. We plan to use cluster randomization. We will have three groups- control, cautionary, resiliency (Jackson, 2005).

9.5 Target Population:

Describe the population to whom the study findings will be generalized

U.S. Military Academy Cadets

9.6 Benefit to the DoD:

State how this study will impact or be of benefit to the Department of Defense

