4. Determine if task-specific self-efficacy is a predictor of performance during CBT by performing a multivariate regression between a single (or multiple) assessments of cadet task-specific self-efficacy, and multiple

measures of performance during CBT including 1) successful completion (pass/fail), 2) Army Combat Fitness Test (ACFT) raw or calculated score, 3) Warrior Competition performance, 4) marksmanship score, 5) written exams, 6) swimming assessment and 7) any other individually graded events.

1. Independent Variable: task-specific self-efficacy scores by event
2. Dependent Variables: performance outcome by event- 1) successful completion (pass/fail), 2) Army Combat Fitness Test (ACFT) score, 3) Warrior Competition performance, 4) marksmanship score, 5) written exams, 6) swimming assessment and 7) any other individually graded events.

5. After completing CBT, determine which sources of self-efficacy (1) enacting mastery experiences, 2) vicarious experiences, 3) verbal persuasion, 4) physiological state, 5) affective state, 6) mental imagery) were the most influential on cadets' self-efficacy throughout CBT specific tasks including 1) successful completion (pass/fail), 2) Army Combat Fitness Test (ACFT) raw or calculated score, 3) Warrior Competition performance, 4) marksmanship score, 5) written exams, 6) swimming assessment and 7) any other individually graded events by conducting a Chi-square test.

1. Independent Variable: task-specific events 1) successful completion (pass/fail), 2) Army Combat Fitness Test (ACFT) score, 3) Warrior Competition performance, 4) marksmanship score, 5) written exams, 6) swimming assessment and 7) any other individually graded events.
2. Dependent Variables: reported level of influence of each (6) source of self-efficacy.

6. Determine the effect of low back pain education (cautionary vs resiliency) on deadlift performance (weight lifted).

We will analyze this with MDL weight lifted as the dependent variable (one-way ANOVA), with a planned comparison analysis if significant differences are found between groups.

7. Determine the degree of confidence cadets have in their ability to succeed at the MDL both before and after the education and MDL

We will analyze if there is a main effect of time in the pre-to-post self-efficacy scores with a paired t-test. We will use multiple regressions to analyze the impact of self-efficacy scores on MDL performance.

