8. Determine the effect of low back pain education (cautionary vs resiliency) on deadlift self-efficacy.

We will analyze change scores with one-way ANOVA with planned comparisons between groups if ANOVA is significant.

9. Determine the effect of low back pain education (cautionary vs resiliency) on perceived spine vulnerability on a deadlift.

We will analyze change scores with one-way ANOVA with planned comparisons between groups if ANOVA is significant.

12.0

Participant Information

12.1 Subject Population:

All incoming US Military Academy cadets, class of '26, attending cadet basic training in the summer of 2022

12.2 AgeRange:

Check all the boxes that apply. If the age range of potential subjects (specimens, records) does not match the range(s) selected, please specify in the text box.

0-17

18-24

25-34

35-44

45-54

55-64

65-74

75+

12.3 Gender:

Male
Female
Other

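### Analyse Objectives 8 and 9 as the post score adjusted for the pre-education score, and fix the deadlift covariates in advance from pre-education measures only

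*Combined protocol and SAP*

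**What the plan says.** For the effect of education on MDL weight, 11.1 states that "we will use ANOVA and planned comparison analysis if between-group differences are found between groups". It adds "We will test groups at baseline to ensure they are similar among important characteristics", and then that "characteristics that are different among groups at baseline or that appear to be influential on load lifted will be included in the ANOVA model". It does not list the characteristics, set a criterion for either route, or say when a covariate must have been measured.

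Item 6 in both 9.3 and 11.6 describes the same analysis without any covariate: "We will analyze this with MDL weight lifted as the dependent variable (one-way ANOVA", followed by planned comparisons if significant.

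Objective 8 is "Determine the effect of low back pain education (cautionary vs resiliency) on deadlift self-efficacy"; Objective 9 asks the same about perceived spine vulnerability. For both, "We will analyze change scores with one-way ANOVA with planned comparisons between groups if ANOVA is significant". No adjustment for the pre score is mentioned.

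Item 7 measures confidence in the deadlift "both before and after the education and MDL" and adds "We will use multiple regressions to analyze the impact of self-efficacy scores on MDL performance", without saying which rating enters the regression.

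Section 10.2 lists gender, weight and deadlift self-efficacy among the data collected. Section 10.14 calls the self-efficacy forms pre-ACFT and post-ACFT. Section 10.1, Phase 3, randomises companies and blinds the data analysts.

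**The concern.** There are two separate points.

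First, a change score carries the measurement noise of both occasions. Comparing post scores adjusted for the pre score answers the same question in a randomised trial with less error variance, using the same two measurements.

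Second, the MDL model cannot be written down in advance. Whether a characteristic influences load lifted can be judged only from MDL data, so that route makes the model depend on outcomes. The baseline-difference route is also settled only by the trial's own data. Nor does the wording limit covariates to those measured before the education. Deadlift self-efficacy is rated again afterwards and is related to MDL in item 7, and Objective 8 asks whether the education changes it. Adjusting MDL for that later rating would remove part of the effect under test. MDL is the outcome on which 11.5 sizes the trial, so its model should be stated once and unambiguously.

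**Working it through.** **Inputs.** From 11.5: 5 kg difference, SD 23 kg, 323 per arm, power 0.80. From 9.4: three arms. Alpha is not stated; 0.05 is assumed. The documents give no pre-post correlation r, covariate R², company variance or number of companies, so every value of these below is an assumption.

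**The plan's own figure.** One-way ANOVA, three groups, f = 0.10: noncentrality f²N = 0.01 × 969 = 9.69 on 2 and 966 df gives power 0.801. The 969 reproduces. The 0.10 is Cohen's f; the standardised difference is 5/23 = 0.217.

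**Objectives 8 and 9.** With equal pre and post SD σ:

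- change-score variance = 2σ²(1−r)
- residual variance of the adjusted post score = σ²(1−r²)
- ratio = (1−r²)/[2(1−r)] = (1+r)/2

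The plan gives no effect size for these objectives, so 0.217 SD is borrowed from MDL. The effect in error-SD units is 0.217/√[2(1−r)] for change and 0.217/√(1−r²) for the adjusted score. Gated power means a significant omnibus F and then a significant cautionary-versus-resiliency comparison, with control midway, 323 per arm and no clustering.

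| r | Variance ratio | Effect/error SD, change vs adjusted | Pairwise power alone | Gated power |
|---|---|---|---|---|
| .5 | 0.75 | 0.217 vs 0.251 | 0.79 vs 0.89 | 0.68 vs 0.81 |
| .7 | 0.85 | 0.281 vs 0.304 | 0.945 vs 0.97 | 0.90 vs 0.94 |
| .8 | 0.90 | 0.344 vs 0.362 | 0.992 vs 0.996 | 0.98 vs 0.99 |

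At company level with 8 companies per arm (df = 24 − 3 = 21), r = .5 and pairwise power alone, the contrast is 0.60 vs 0.69 at company variance .01 and 0.33 vs 0.35 at .05.

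**MDL, precision.** With a fixed baseline list the effect becomes 0.217/√(1−R²). Gated power without clustering is 0.680 for the bare one-way ANOVA, and 0.731, 0.842 and 0.945 at R² of .1, .3 and .5. The 11.1 rule itself was simulated with both routes at p<.05 and predictive baseline covariates on offer. It gave 0.728 against 0.730 for a fixed list at R² = .1, and 0.837 against 0.837 at .3. The fixed list therefore gains over the bare ANOVA of 9.3 and 11.6, but not over the 11.1 rule.

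**MDL, type I error.** Null simulations at R² of .1/.3/.5, four baseline covariates, no clustering:

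- 11.1 rule applied mechanically at p<.05: omnibus 0.051/0.047/0.050; gated comparison 0.024/0.021/0.024
- reporting the better of the unadjusted and fully adjusted models: omnibus 0.067/0.078/0.083; gated comparison 0.033/0.037/0.041

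**MDL, if a post-education rating were used.** Let ρ be its correlation with MDL and s the shift in SD caused by the education. The adjusted effect is 5 − ρ × 23 × s, with residual SD 23√(1−ρ²). Unadjusted pairwise power at 323 per arm is 0.789.

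- ρ = .2, s = .1: 5 − 0.46 = 4.54 kg, power 0.726
- ρ = .2, s = .2: 5 − 0.92 = 4.08 kg, power 0.633
- ρ = .5, s = .3: 5 − 3.45 = 1.55 kg, power 0.166

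**The case against.** The strongest reply is that 11.1 already brings influential covariates into the MDL model, that blinded analysts cannot easily steer it toward an arm, and that the short entries in 9.3 and 11.6 are summaries which 11.1 elaborates. Most of this stands. A reader might infer that the 11.1 rule costs power or inflates type I error. The simulations support neither when the rule is applied mechanically to baseline covariates, and even free choice between two models left the gated comparison below 5%. What remains is that 11.1 states no mechanical rule. Blinding limits bias toward an arm but does not fix a model.

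A reader might also infer that the plan intends to adjust MDL for the post-education rating. The documents do not say so. The sentence follows one about baseline testing and is aimed at confounding, and self-efficacy has its own regression in item 7. Baseline-only is the more natural reading of the word used. The point is only that the other reading is not excluded, and excluding it takes a few words.

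On Objectives 8 and 9, it is fair to say that the change-score ANOVA is unbiased under randomisation, that r is unknown, and that the gain is negligible at r of .8 or above. All of that stands; the case is precision at no cost. It is also true that 10.2 lists no spine-vulnerability measure, so for Objective 9 the two scores are inferred from the planned change score.

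**Conclusion.** This is a worthwhile, almost free improvement, not the correction of an invalid analysis.

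For Objectives 8 and 9 the gain is a 10 to 25% reduction in error variance for r between .8 and .5. This assumes equal pre and post SDs; the corresponding power figures also assume a borrowed effect size and no clustering. With company clustering the power gain is smaller.

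For MDL the reasons to change are specification, not power: the model should not wait on outcomes, 11.1 should agree with 9.3 and 11.6, and post-education covariates should be expressly barred. The loss from such a covariate is conditional on its ever being used and spans 0.46 to 3.45 kg of the 5 kg over the values tried.

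A reader might hope that covariate adjustment makes up for randomising whole companies. It does not. Clustering is a separate issue that these changes leave open.

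**What to change.** 1. **Objectives 8 and 9 (9.3, 11.1, 11.6).** Replace the change-score ANOVA with a between-arm comparison of the post score adjusted for the pre score, keeping whatever allowance for company randomisation the main analysis uses. State that the pre score is taken before the education, since 10.14 ties the forms only to the ACFT.

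2. **MDL (11.1, with item 6 of 9.3 and 11.6 brought into line).** Replace both data-dependent routes with a short covariate list fixed before any MDL data are seen and limited to measures taken before the education. Gender and body weight are examples already collected under 10.2. The documents do not show that they predict MDL; the lab data cited in 11.5 could be used to check this if they hold those variables. Deadlift self-efficacy may enter only as the pre-education rating. Report the unadjusted result as a sensitivity analysis, and show baseline characteristics by arm without tests.

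3. **Missing covariates.** State one simple rule.

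The cost is wording in three sections and a few degrees of freedom. No new data are needed beyond the pre and post scores that the change scores already require.

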11.5 Please provide a justification for your sample size

We have powered this study to determine a between-group difference of 5kg. This is equivalent to an effect size of $d=.10$ given a standard deviation of 23kg (available from previously collected data in this lab). We used G*Power 3.0 with power at .80 to calculate a total sample size of 969 subjects (323 per group). We will therefore attempt to recruit 1200 participants, allowing for 20% injury or attrition which might prevent subjects from completing the MDL event during CBT ACFT.

11.6 Data Analysis Plan: Complete description: Background, Objectives, Design, Step by Step how the project is going to be done, Data analysis plan:

1. Determine if general self-efficacy is a predictor of injury during CBT by performing a Kaplan-Meier Survival Curve, a single assessment (Cadet General Self-Efficacy Assessment), analysis of the Defense Medical Surveillance System (DMSS) and a follow-up self-reported injury assessment.
 1. Independent Variable: Cadet General Self-Efficacy score
 2. Dependent Variables: Injury report according to DMSS or self-reported
2. Determine if task-specific self-efficacy is a predictor of injury during specific CBT events by performing a Kaplan-Meier Survival Curve, a single (or multiple) assessments of cadet task-specific self-efficacy, analysis of the Defense Medical Surveillance System (DMSS) and a follow-up self-reported injury assessment.
 1. Independent Variable: Cadet Task-Specific Self-Efficacy score
 2. Dependent Variables: Injury report according to DMSS or self-reported
3. Determine if general self-efficacy is a predictor of performance during CBT by performing a multivariate regression between a single assessment (Cadet General Self-Efficacy Assessment) and multiple measures of performance during CBT including 1) successful completion (pass/fail), 2) Army Combat Fitness Test (ACFT) raw or calculated score, 3) Warrior Competition performance, 4) marksmanship score, 5) written exams, 6) swimming assessment and 7) any other individually graded events.
 1. Independent Variable: Cadet General Self-Efficacy score
 2. Dependent Variables: performance outcome by event- 1) successful completion (pass/fail), 2) Army Combat Fitness Test (ACFT) score, 3) Warrior Competition performance, 4) marksmanship score, 5) written exams, 6) swimming assessment and 7) any other individually graded events.
4. Determine if task-specific self-efficacy is a predictor of performance during CBT by performing a multivariate regression between a single (or multiple) assessments of cadet task-specific self-efficacy, and multiple

measures of performance during CBT including 1) successful completion (pass/fail), 2) Army Combat Fitness Test (ACFT) raw or calculated score, 3) Warrior Competition performance, 4) marksmanship score, 5) written exams, 6) swimming assessment and 7) any other individually graded events.

1. Independent Variable: task-specific self-efficacy scores by event
2. Dependent Variables: performance outcome by event- 1) successful completion (pass/fail), 2) Army Combat Fitness Test (ACFT) score, 3) Warrior Competition performance, 4) marksmanship score, 5) written exams, 6) swimming assessment and 7) any other individually graded events.

5. After completing CBT, determine which sources of self-efficacy (1) enacting mastery experiences, 2) vicarious experiences, 3) verbal persuasion, 4) physiological state, 5) affective state, 6) mental imagery) were the most influential on cadets' self-efficacy throughout CBT specific tasks including 1) successful completion (pass/fail), 2) Army Combat Fitness Test (ACFT) raw or calculated score, 3) Warrior Competition performance, 4) marksmanship score, 5) written exams, 6) swimming assessment and 7) any other individually graded events by conducting a Chi-square test.

1. Independent Variable: task-specific events 1) successful completion (pass/fail), 2) Army Combat Fitness Test (ACFT) score, 3) Warrior Competition performance, 4) marksmanship score, 5) written exams, 6) swimming assessment and 7) any other individually graded events.
2. Dependent Variables: reported level of influence of each (6) source of self-efficacy.

6. Determine the effect of low back pain education (cautionary vs resiliency) on deadlift performance (weight lifted).

We will analyze this with MDL weight lifted as the dependent variable (one-way ANOVA), with a planned comparison analysis if significant differences are found between groups.

7. Determine the degree of confidence cadets have in their ability to succeed at the MDL both before and after the education and MDL

We will analyze if there is a main effect of time in the pre-to-post self-efficacy scores with a paired t-test. We will use multiple regressions to analyze the impact of self-efficacy scores on MDL performance.

8. Determine the effect of low back pain education (cautionary vs resiliency) on deadlift self-efficacy.

We will analyze change scores with one-way ANOVA with planned comparisons between groups if ANOVA is significant.

9. Determine the effect of low back pain education (cautionary vs resiliency) on perceived spine vulnerability on a deadlift.

We will analyze change scores with one-way ANOVA with planned comparisons between groups if ANOVA is significant.

12.0

Participant Information

12.1 Subject Population:

All incoming US Military Academy cadets, class of '26, attending cadet basic training in the summer of 2022

12.2 AgeRange:

Check all the boxes that apply. If the age range of potential subjects (specimens, records) does not match the range(s) selected, please specify in the text box.

0-17

18-24

25-34

35-44

45-54

55-64

65-74

75+

12.3 Gender:

Male
Female
Other

